### 7.6. Demographic and Other Baseline Characteristics

The following characteristics will be collected at baseline and summarized in descriptive tables for the analysis cohort:

- Age (years)
- Gender
- Height, weight, body mass index (BMI), heart rate, blood pressure
- Left ventricular ejection fraction (%) and LVEF method of measurement (baseline CRF)
- ECG: QRS duration, PR interval, RR interval, QTc interval (baseline CRF)

- NYHA classification
- Medical history
- Cardiovascular medications
- Left ventricular ejection fraction, left ventricular end systolic volume, left ventricular end diastolic volume (MUO MRI CRF)

BMI will be calculated as weight in kg/(height in m). Age will be calculated by the following formula: year of enrollment – year of birth. The year of enrollment will be determined from the date of informed consent. Only “difficult” CRT patients are selected for this study in order to adequately address the potential benefit of MultiSpot Pacing in this patient population. The term “difficult” represent those patients with an increased likelihood of non-response to conventional cardiac resynchronization therapy (e.g. ischemic patients or non-LBBB left ventricular dyssynchrony patients).

The characteristics of the “difficult” CRT patient population will be summarized with regard to typical CRT response indicators in a table similar to the table below. The table cohort will be all enrolled patients and the analysis cohort.

**Table 4: Subject Characteristics – CRT Response Indicators**

Subject Characteristics	Total Subjects For Analysis (N = Z)	Total Subjects (N = 40)
No Left Bundle Branch Block	N (%)	N (%)
QRS duration (ms)		
Mean (SD)	x (x)	x (x)
Median	x	x
25 th Percentile – 75 th Percentile	x (x)	x (x)
Minimum – Maximum	x (x)	x (x)
QRS duration ≤ 150 ms	N (%)	N (%)
Amount of Scar (%)		
Mean (SD)	x (x)	x (x)
Median	x	x
25 th Percentile – 75 th Percentile	x – x	x – x
Minimum – Maximum	x – x	x – x
Number of Subjects with Measure Available	N (%)	N (%)
LBBB and QRS area above > 150 ms and myocardial scar	N (%)	N (%)
Amount of scar (%)		
Mean (SD)	x (x)	x (x)
Median	x	x
25 th Percentile – 75 th Percentile	x – x	x – x
Minimum – Maximum	x – x	x – x

Subject Characteristics	Total Subjects For Analysis (N = Z)	Total Subjects (N = 40)
Total (No LBBB or QRS $\leq$ 150 or (LBBB and QRS $>$ 150 and myocardial scar))	N (%)	N (%)

## 7.7. Treatment Characteristics

For the EP study visit, three leads will be placed, namely one in the right atrium, one in the right ventricle and one in the left ventricle. A second left ventricular lead may be placed to reach the LV apex. The locations of these leads will be summarized.

For the EP study visit, the following variables will be summarized in descriptive tables:

- Procedure time (minutes) (from EP study CRF)
- Type of procedure after EP study visit
- RA, RV, LV transvenous lead I and lead II positions if applicable (from EP study CRF and/or fluoroscopy images)
- Types of LV transvenous lead I and II if applicable
- Atrial pacing rate (beats per minutes)
- Time between atrial pace and RV sense (AV timing)
- Time between atrial pace and end of P-wave
- Calculated optimal AV delay based on CardioSync™ formula
- VV delays in case of sequential pacing per electrode (apical, mid, basal electrode)

Cardiovascular medications are collected at baseline and will be summarized. Medications will be coded into medication categories. The number of medications in each category, and the number and percentage of subjects with medications in each category will be summarized.

## 7.8. Interim Analyses

No interim analysis is planned for this study.

## 7.9. Evaluation of Objectives

### 7.9.1. Primary Objective #1

Compare the hemodynamic response of a MultiSpot-SYN Left Ventricular pacing configuration (simultaneous LV pacing) to a single spot LV pacing configuration in patients undergoing a research study, an EP exploratory procedure or CRT implant using the contractility parameter positive LV dP/dt max.

### 7.9.1.1. Hypothesis

It is hypothesized that MultiSpot pacing simultaneously is superior to BiV pacing. The null and alternative hypotheses are:

$$H_0: \Delta_{\text{MultiSpot SYN}} - \Delta_{\text{BiV}} = 0\%$$

$$H_1: \Delta_{\text{MultiSpot SYN}} - \Delta_{\text{BiV}} \neq 0\%$$

where  $\Delta$  indicates percentage change from baseline for the respective pacing configuration. The hypothesis will be assessed for the following three comparisons: MultiSpot SYN to BiV basal (standard CRT), MultiSpot SYN to BiV mid, and MultiSpot SYN to BiV apical. In particular, the comparison of MultiSpot SYN to standard CRT is of interest.

### 7.9.1.2. Endpoint Definition

The contractile ability of LV is characterized by the positive LV dP/dt max. An increase in contractility is manifested as an increase in dP/dt max during isovolumic contraction. It is a measure of the initial velocity of myocardial contraction and is a derivative of the LV-pressure. LV pressure is measured invasively during the EP visit using a catheter inside the LV.

The endpoint is % change LV dP/dt max from baseline (AAI pacing) to correct for baseline differences and drifts. This percentage change is calculated as  $([\text{median dP/dt max during pacing On}] - [\text{median baseline dP/dt max during pacing Off}]) / [\text{median dP/dt max during pacing Off}]$ . Pacing Off denotes here AAI pacing (CRT pacing off). In general, eight non-ectopic beats will be considered during baseline and during pacing On to calculate the medians during baseline and the pacing On settings. If less than eight beats will be available, the maximum number of available beats will be used for calculation of the median. For each combination of pacing configuration and AV delay, there are four repetitions of pacing On/Off and thus eight percentage changes will be calculated per combination.

Other endpoints, e.g., blood pressures, might be considered instead of LV dP/dt max in an exploratory secondary analysis for this objective.

### 7.9.1.3. Analysis Methods

#### A. Statistical Methodology

The following steps will be applied for analysis.

1. Regression model per patient
2. Use the parameter estimates from regression model to obtain predicted maximum response and corresponding best AV delay per configuration
3. Use PROC GLM to obtain the standard error of the predicted maximum response
4. Perform weighted t-test for comparison between configurations

#### Step 1

For each patient, a regression analysis will be performed to model % change LV dP/dt max dependent on configuration and AV delay. The model will include effects for configuration, for AV delay up to a quadratic order, and interaction effects. AV delay will have values 0, -30, +30, -60, 60 ms to indicate the difference between the applied AV delay and the optimal AV delay based on the Cardio Sync formula. AV delay will be treated as a continuous variable. The following regression model will be applied for each subject:

$$\begin{aligned} \% \text{ change} = & \beta_1 * \text{Configuration}_1 + \beta_2 * \text{Configuration}_2 + \beta_3 * \text{Configuration}_3 + \beta_4 * \text{Configuration}_4 + \\ & \beta_5 * \text{Configuration}_5 + \beta_6 * \text{AVdelay} + \beta_7 * \text{AVdelay}^2 + \beta_8 * \text{Configuration}_1 * \text{AVdelay} + \beta_9 * \\ & \text{Configuration}_2 * \text{AVdelay} + \beta_{10} * \text{Configuration}_3 * \text{AVdelay} + \beta_{11} * \text{Configuration}_4 * \text{AVdelay} + \beta_{12} * \end{aligned}$$

$$\text{Configuration}_5 * \text{AVdelay} + \beta_{13} * \text{Configuration}_1 * \text{AVdelay}^2 + \beta_{14} * \text{Configuration}_2 * \text{AVdelay}^2 + \beta_{15} * \text{Configuration}_3 * \text{AVdelay}^2 + \beta_{16} * \text{Configuration}_4 * \text{AVdelay}^2 + \beta_{17} * \text{Configuration}_5 * \text{AVdelay}^2 + \varepsilon.$$

Configurationi is 1 if at time point t pacing configuration i is performed and 0 otherwise. The error is denoted by ε. For ease of interpretation, no intercept is included in the model such that the estimate βi correspond to the estimated mean % change during configuration i. Alternatively, one could include an intercept which would then model a reference configuration.

[REDACTED]

[REDACTED]

[REDACTED]

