Endpoint for the primary objective 1, primary objective 2 and secondary objective 1 will be % change LV dP/dt max from baseline. This percentage change is calculated as $([\text{median dP/dt max during pacing On}] - [\text{median baseline dP/dt max during pacing Off}]) / [\text{median dP/dt max during pacing Off}]$. This endpoint will be used primarily to evaluate the hypothesis of objective 1, primary objective 2 and secondary objective 1. Other endpoints, e.g., blood pressures, might be included in an exploratory secondary analysis for these objectives.

H.1.1 Primary objective 1

Compare the hemodynamic response of a MultiSpot-SYN Left Ventricular pacing configuration (simultaneous LV pacing) to a single spot LV pacing configuration in patients undergoing a research study, an EP exploratory procedure or CRT implant using the contractility parameter positive LV dP/dt max.

It is hypothesized that MultiSpot SYN (pacing on all 3 LV electrodes simultaneously) is superior to conventional BiV pacing (i.e. using only the basal LV electrode).

The null and alternative hypotheses are:

$$H_0: \Delta_{\text{MultiSpot SYN}} - \Delta_{\text{BiV}} = 0\%$$

$$H_1: \Delta_{\text{MultiSpot SYN}} - \Delta_{\text{BiV}} \neq 0\%,$$

where Δ indicates percentage change from baseline for the respective pacing configuration.

For each patient, a regression analysis will be performed to model % change LV dP/dt max dependent on configuration and AV delay. Based on the fitted model for each patient, the best AV delay for each configuration will be determined together with the predicted % change at this best AV delay. This best AV delay may differ from the optimal AV delay determined by the CardioSync formula. Paired two-sided t-tests will be used to evaluate whether there is a statistical significant difference between MultiSpot-SYN and standard BiV pacing. Instead of paired t-tests, a Wilcoxon signed rank test might be performed if normality is violated.

H.1.2 Primary objective 2

Compare the hemodynamic response of a MultiSpot-SEQ Left Ventricular pacing configuration (sequential LV pacing) to a single spot LV pacing configuration in patients undergoing a research study, an EP exploratory procedure or CRT implant using the contractility parameter positive LV dP/dt max.

It is hypothesized that MultiSpot SEQ (pacing on 3 LV electrodes activated sequentially from apex to mid and then to base) is superior to conventional BiV pacing (i.e. using only the basal LV electrode).

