**Step 2**

R code similar to the code below can be used to determine the AV delay (best AV delay) which leads to the maximum predicted response based on the fitted model for each patient.

[REDACTED]

[REDACTED]

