**Table 8: Percentage Change LV dP/dt max per configuration**

Comparison	Number of Subjects	Difference in % change LV dP/dt max	95 % Confidence interval
BiV basal	N	x.xx	x.xx – x.xx
BiV mid	N	x.xx	x.xx – x.xx
BiV apical	N	x.xx	x.xx – x.xx
MultiSpot SYN	N	x.xx	x.xx – x.xx
MultiSpot SEQ	N	x.xx	x.xx – x.xx

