**Table 10: Difference between optimal AV delay and best AV delay**

	BiV basal (N =X)	BiV mid (N =X)	BiV distal (N =X)	MultiSpot SYN (N =X)	MultiSpot SEQ (N =X)
Difference between optimal AV delay and best AV delay					
Mean ± Standard Deviation	X ± Y	X ± Y	X ± Y	X ± Y	X ± Y
Median	X	X	X	X	X
25 th Percentile – 75 th Percentile	X – Y	X – Y	X – Y	X – Y	X – Y
Minimum – Maximum	X - Y	X - Y	X – Y	X - Y	X - Y
Number of Subjects With Measure Available (N,%)	X (Y%)	X (Y%)	X (Y%)	X (Y%)	X (Y%)
Difference between % change LV dP/dt max at optimal AV delay and at best AV delay					
Mean ± Standard Deviation	X ± Y	X ± Y	X ± Y	X ± Y	X ± Y
Median	X	X	X	X	X
25 th Percentile – 75 th Percentile	X – Y	X – Y	X – Y	X – Y	X – Y
Minimum – Maximum	X - Y	X - Y	X – Y	X - Y	X - Y
Number of Subjects With Measure Available (N,%)	X (Y%)	X (Y%)	X (Y%)	X (Y%)	X (Y%)

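### Scoring each configuration at the peak of its own fitted AV curve makes Table 10's response gap non-positive by construction and, if the curve is near quadratic, tends to inflate Table 8; add the same results at the CardioSync delay

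*SAP*

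**What the plan says.** SAP 7.9.1.3, Step 1, fits one regression per patient: "The model will include effects for configuration, for AV delay up to a quadratic order, and interaction effects". Each configuration therefore has its own quadratic. The delays enter as offsets from the CardioSync delay: "AV delay will have values 0, -30, +30, -60, 60 ms". The list of steps gives Step 2 as "Use the parameter estimates from regression model to obtain predicted maximum response and corresponding best AV delay per configuration". Its detailed text is to "determine the AV delay (best AV delay) which leads to the maximum predicted response based on the fitted model for each patient", and the predicted value at that delay is carried forward as the patient's score. Protocol H.1.1 has the same rule: "the best AV delay for each configuration will be determined together with the predicted % change at this best AV delay".

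Step 3 obtains a standard error at the chosen delay, and the stated purpose is to give imprecise patients less weight. Step 4 compares configurations with a weighted t-test.

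The scores feed Table 8 ("Percentage Change LV dP/dt max per configuration", with 95% CIs), the comparison Tables 9, 11 and 12, and Table 10, which includes the "Difference between % change LV dP/dt max at optimal AV delay and at best AV delay". The text that can be read contains no correction for choosing the maximum and no configuration comparison at the fixed CardioSync delay.

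**The concern.** A fitted peak contains the noise that helped to make it the peak. When the true curve is quadratic, the expected fitted maximum exceeds the true maximum, by more when the curve is flat or the data are noisy. AAI pacing is not optimised over AV delay, so a % change from AAI carries the whole excess.

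Three results are affected to different degrees:

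- **Table 10** could be read as evidence that CardioSync misses the optimum when it does not.
- **Table 8** could overstate each configuration's response, with intervals that are too optimistic. Both documents expect the study to supply data for designing later studies, so the overstatement could be carried forward.
- **Tables 9, 11 and 12** compare two scores built by the same rule. They are distorted only if the two excesses differ.

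**Working it through.** **The plan's own figure.** Paired difference 3.5, SD 7, two-sided 0.05, 80% power (SAP 6.1). The normal approximation gives n = (1.96 + 0.84)² × 7² / 3.5² ≈ 31.4. The noncentral t gives n = 34 with 80.8% power. For SEQ (difference 4) power at 34 is 89.9%, against 90% stated. The sample size is sound and is not in question.

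**Why Table 10's gap cannot be positive.** Write one configuration's fitted curve as b0 + b1·x + b2·x², with x = offset/60 ms. The fitted value at CardioSync is b0. With an interior peak (b2 < 0) the maximum is b0 + b1²/(4|b2|), which is at least b0. If the maximum is at an edge, it is still at least the value at x = 0, because 0 lies in the search range. In simulation the maximum was at or above b0 in 100% of fits. Even when the true b1 is 0, its estimate is not exactly 0, so the mean gap is negative. This takes both values from the same fitted curve, as Step 2 implies.

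**Noise of one mean.** SAP 7.9.1.2 says "there are four repetitions of pacing On/Off and thus eight percentage changes will be calculated per combination". I read this as 4 On and 5 Off periods, with each On paired with its two neighbouring Offs. If one % change has SD σ, each period contributes variance σ²/2. In the mean of eight changes each On counts twice, the three inner Offs twice and the two outer Offs once:

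variance = (σ²/2) × (4×4 + 3×4 + 2×1)/64 = (σ²/2) × 30/64 = 0.234σ²

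This is worth about 4.3 independent changes. For σ = 3, 5 and 8 the SD of the mean is 1.45, 2.42 and 3.87 points.

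**Assumptions not in the documents.** σ of 3, 5 or 8 points; curvature, expressed as the fall at ±60 ms; true peak at offset 0 unless stated; search within ±60 ms.

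**Upward bias of one configuration's score (simulation of Steps 1–2).**

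| Fall at ±60 ms | σ = 3 | σ = 5 | σ = 8 |
|---|---|---|---|
| Flat | 1.1 | 1.9 | 3.0 |
| 2 points | 0.3 | 0.8 | 1.9 |
| 4 points | 0.1 | 0.3 | 1.1 |

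With the true peak at CardioSync, these are also the mean apparent shortfalls in Table 10.

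**Table 8 intervals.** With n = 34, between-patient SD 7 and a 2-point fall, the 95% CI misses the true value in about 6%, 10–11% and 30–31% of trials.

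**Departure from a quadratic.** Take a tent-shaped curve falling linearly by 4 points to ±60 ms, with values −4, −2, 0, −2, −4. The five-point quadratic gives offset 0 the weights (−3, 12, 17, 12, −3)/35. The fitted peak is then (12 − 24 + 0 − 24 + 12)/35 = −24/35 = −0.69, against a true peak of 0. After adding the selection effect the net bias is about −0.6, −0.2 and +0.6 points.

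**Comparisons with equal true maxima, n = 34, total SD of the difference about 7.**

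| BiV fall vs MultiSpot fall | False gain (σ = 3, 5, 8) | Type I error |
|---|---|---|
| 4 vs 4 | 0 | about 5% |
| 4 vs 2 | 0.2, 0.5, 0.8 | about 5–10% |
| 4 vs 1 | 0.5, 0.9–1.0, 1.3 | about 7–18% |

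The 4 vs 2 gains are the differences between rows of the bias table: 0.3 − 0.1, 0.8 − 0.3 and 1.9 − 1.1. These error rates come from unweighted tests; in a separate set of runs, inverse-variance weighting changed the bias by no more than about 0.16 points.

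**Offset 0 is a different question.** If SYN truly peaks at +30 ms and falls 4 points over 60 ms, it loses 4 × (30/60)² = 1.0 point at offset 0. With equal true maxima and BiV peaking at 0, the offset-0 comparison shows SYN 1.0 point worse and rejects in about 12% of trials. The planned maximum gives about +0.2 to +0.3 points and 5–6%.

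**The case against.** A reader might infer that the primary comparison is biased towards MultiSpot pacing. The documents do not support that. Both configurations are optimised by the same rule, nothing states that three-site pacing flattens the AV response, and with equal shape and noise the difference is unbiased. Against this, the model fits separate AV terms for each configuration, so the plan does not assume equal shapes either. The comparison result is therefore conditional.

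A reader might also infer that Table 8 must be too high, or that offset 0 is the unbiased answer. Neither follows. A peaked curve can offset or reverse the bias. Offset 0 is neutral only if the true peaks lie equally close to CardioSync. Protocol H.1.1 itself expects best and CardioSync delays to differ, and Protocol C.5 defines standard BiV with an individually optimised AV delay. This is good reason to keep the best-AV score as primary.

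Tables 8 and 10 together already let a reader approximate offset-0 means, exactly only if weights and patient numbers match. They give no interval or P-value for a comparison at that delay.

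The code for these steps is blacked out and some text before Table 8 is not available, so the search range and any correction cannot be seen. This limits the claims about size. It does not alter the Table 10 result while offset 0 remains a candidate.

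The exploratory label is the plan's reason for not adjusting for multiplicity; it does not deal with a biased estimate.

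**Conclusion.** The point holds in a limited form. It is certain that Table 10's response gap is non-positive by construction when both values come from one fit, so it cannot alone show a CardioSync shortfall. If the AV response is near quadratic, Table 8's best-AV % changes are biased upward and their CIs under-cover. For moderate curvature the bias runs from about 0.1 points (SD 3, 4-point fall) to 1.9 points (SD 8, 2-point fall), and is larger for a flat curve. The sign can reverse for a sharply peaked one.

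For the planned comparisons there is a possible distortion, not a demonstrated one. It is zero with equal shapes and noise. It is 0.2–0.8 points in the milder unequal case and 0.5–1.3 in the stronger one, or 6–23% and 14–37% of the 3.5-point design effect. All sizes rest on assumed noise and curvature, because the documents give neither.

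**What to change.** 1. Keep the best-AV analysis as primary in SAP 7.9.1.3.
2. In Table 8, add each configuration's estimate and 95% CI at AV offset 0. In Tables 9, 11 and 12, add the same comparisons at offset 0 with 95% CI and P-value. Label them a pre-specified sensitivity analysis. State that this is a different estimand, which can favour the configuration whose peak lies nearer the CardioSync delay.
3. Under Table 10, state that the response gap is non-positive by construction and so does not by itself show a CardioSync shortfall.
4. Cross-fitted values (delay chosen on three repetitions, response read from the fourth, averaged over the four) are optional. At noise SD 5 they still leave about +0.45 points of bias for a flat curve and −0.40 for a 2-point fall.

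The planned model already estimates the offset-0 values, so no new data or patients are needed. The cost is a little programming, extra table rows and a second result to interpret, which may disagree with the primary one.

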**Step 3**

Within SAS, PROC GLM can be used to determine the standard error of the predicted change dP/dt max at best AV delay δ, i.e., the standard error of the predicted maximum change dP/dt max. We would like to take this standard error into account since subjects with less precise estimates of maximum LV dP/dt max should have less influence in the following comparison between configurations. [REDACTED]

[REDACTED]

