### 7.9.2.3. Analysis Methods

#### A. Statistical Methodology

Statistical analysis will use the methods described for the primary objective 1, with MultiSpot-SYN LV pacing replaced by MultiSpot-SEQ LV pacing configuration.

Results will be summarized in a table similar to the table below:

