### 7.9.3.3. Analysis Methods

#### A. Statistical Methodology

Statistical analysis will use the methods described for the primary objective 1, with single spot LV pacing configuration (standard BiV) replaced by MultiSpot-SEQ LV pacing.

Inferiority testing will be performed one-sided at a significance level of 0.025. Non-inferiority of MultiSpot SEQ to MultiSpot SYN will be declared if the lower limit of a two-sided 95% confidence interval for the mean difference between MultiSpot SEQ and SYN does not fall below -3%. Superiority testing will be performed two-sided at a significance level of 0.05.

Results for non-inferiority testing will be summarized in a table similar to the table below:

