### **7.12. Changes to Planned Analysis**

This Statistical Analysis Plan does not deviate from the planned statistical analysis in the CIP. The analysis cohort has been described in the CIP as follows: "The Analysis Population is defined as patients, who are enrolled, have no inclusion or exclusion criteria violation regarding the most important criteria, i.e., inclusion criteria 1 and 2 and exclusion criterion 3, and for whom the EP procedure could be completed successfully." This definition has been clarified in the SAP to the following definition: "The Analysis Population is defined as patients who are enrolled, have no inclusion or exclusion criteria violation regarding the most important criteria, i.e., inclusion criteria 1 and 2 and exclusion criterion 3, and have less than 3 months between MRI and EP visit."

Any change to the data analysis methods described in the Clinical Investigational Plan will require an amendment only if it changes an objective of the Clinical Investigational Plan. Any other change to the data analysis methods described in the Clinical Investigational Plan and this Statistical Analysis Plan, and the justification for making the change, will be described in the clinical study report. Additional exploratory analyses of the data will be conducted as deemed appropriate.

---

**8.** [REDACTED]

[REDACTED]

[REDACTED]

[REDACTED]

[REDACTED]

[REDACTED]	[REDACTED]	[REDACTED]
[REDACTED]	[REDACTED]	[REDACTED]
[REDACTED]	[REDACTED]	[REDACTED]
[REDACTED]	[REDACTED]	[REDACTED]
[REDACTED]	[REDACTED]	[REDACTED]
[REDACTED]	[REDACTED]	[REDACTED]
[REDACTED]	[REDACTED]	[REDACTED]

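### The SAP replaces the protocol's unweighted paired t-test with a weighted t-test for both primary objectives and the non-inferiority comparison, while SAP 7.12 says nothing deviates

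*SAP*

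**What the plan says.** **Protocol H.1.1.** A regression in each patient gives the predicted % change at the best AV delay for each configuration. The comparison is then: "Paired two-sided t-tests will be used to evaluate whether there is a statistical significant difference between MultiSpot-SYN and standard BiV pacing". One alternative is named: "Instead of paired t-tests, a Wilcoxon signed rank test might be performed if normality is violated". Weighting is not mentioned.

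**SAP 7.9.1.3.** The regression and the predicted maximum are kept. Step 3 adds the standard error (SE) of that maximum, because "subjects with less precise estimates of maximum LV dP/dt max should have less influence in the following comparison between configurations". Step 4 in the list of steps reads "Perform weighted t-test for comparison between configurations".

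**Carry-over.** SAP 7.9.2.3, for primary objective 2: "Statistical analysis will use the methods described for the primary objective 1, with MultiSpot-SYN LV pacing replaced by MultiSpot-SEQ LV pacing configuration". SAP 7.9.3.3, for secondary objective 1, also uses the objective 1 methods, "with single spot LV pacing configuration (standard BiV) replaced by MultiSpot-SEQ LV pacing". Non-inferiority is declared if the "lower limit of a two-sided 95% confidence interval for the mean difference between MultiSpot SEQ and SYN does not fall below -3" per cent.

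**Declared changes.** SAP 7.12 opens: "This Statistical Analysis Plan does not deviate from the planned statistical analysis in the CIP". The only difference it then discusses is the wording of the Analysis Population.

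**Sample size.** SAP 6.1 to 6.3 repeat Protocol C.7: 34 patients, an SD of 7% for the difference, and power of 80%, 90% and 80%. No weighting term appears.

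**The concern.** Weighting by precision changes both the estimate of the mean difference and its variance, so these are two different tests of the same hypotheses. They can give different p-values, and a different lower limit to set against the -3% margin. The section meant to record such changes says there are none, so nothing in the plan tells a reader which test governs. The power statement belongs to the test that the SAP no longer lists. The error rate of a weighted t-test also depends on how the weights are built, which the unweighted test largely avoids.

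**Working it through.** **1. Which test do the stated powers belong to?** Inputs from SAP 6.1 to 6.3: n = 34, SD of the difference 7, two-sided 0.05 (one-sided 0.025 for non-inferiority). For an unweighted paired t-test with 33 df, the noncentrality is (effect / SD) × √n.

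| Comparison | Noncentrality | Power | Stated |
|---|---|---|---|
| Objective 1, effect 3.5 | 3.5/7 × √34 = 2.92 | 80.8% | 80% |
| Objective 2, effect 4 | 4/7 × √34 = 3.33 | 89.9% | 90% |
| Non-inferiority, 0.5 - (-3) = 3.5 | 3.5/7 × √34 = 2.92 | 80.8% | 80% |

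The normal approximation would need only 32 and 33 patients for the two primary objectives. A two-independent-sample calculation would need 63 per arm for objective 1. Section 6 was therefore sized on the protocol's unweighted paired t-test.

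**2. Would the weights differ between patients?** SAP 5.3.1 and 7.9.1.2 give five AV delays (0, ±30, ±60 ms) and eight values per combination. SAP 7.9.1.3 fits a quadratic in AV delay for each configuration. With x = AV delay/30, the SE of a prediction is σ√(h/8), where h = 1/5 + x²/10 + (x² - 2)²/14:

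- 0 ms: h = 17/35
- ±30 ms: h = 13/35
- ±60 ms: h = 31/35

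The SE at ±60 ms is √(31/13) = 1.54 times that at ±30 ms, even with identical noise in every patient. This assumes independent values and a maximum searched within ±60 ms. The ratio is for one configuration. For the paired difference the variance goes with the sum of two h values, and the spread is smaller: coefficients of variation (CV) of the SE of 8.2%, 11.1% and 18.3% in the three scenarios tried (best AV delay uniform on ±60 ms, independent between configurations; the same but shared; 30% of patients at ±60 ms).

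**3. Type I error if the weights are 1/SE² (assumed).** Let d_i vary with variance τ² + SE_i², total 49. Take m = Σwd/Σw, s² = Σw(d - m)²/(n - 1), variance s²/Σw, 33 df. If τ² dominates, the true variance of m is close to τ²/n_eff, with n_eff = (Σw)²/Σw², while the formula behaves as if it were τ²/n. At an SE CV of 30%, n_eff is about 25 of 34.

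*AV-delay position only, identical noise* (100,000 simulated trials each): 5.03%, 5.22%, 5.53% if half the variance is between patients; 5.18%, 5.41%, 5.75% if 90% is.

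*Noise also differing between patients, illustrative SE CV 30%* (40,000 trials each; the documents give no SEs):

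| Noise share of variance | Type I error | Power, objective 1 | Power, objective 2 |
|---|---|---|---|
| 5% | 9.1% | 78.5% | 86.8% |
| 10% | 9.0% | 78.5% | 87.6% |
| 25% | 8.4% | 80.5% | 88.8% |
| 50% | 7.6% | 84.4% | 92.0% |
| 90% | 5.7% | 90.1% | 95.9% |

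If all spread is measurement noise, error is 5.0-5.2% at every CV tried. With weights 1/(estimated between-patient variance + SE²) it is 4.7-5.4%. For the unweighted test it is 4.8-5.1% at CVs up to 50%.

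**The case against.** The strongest reply is that the protocol leaves detailed methods to the SAP (section H), and that H.1 requires an amendment only if an objective changes. The within-patient comparison of predicted maxima is kept, and SAP Step 3 gives an open, sensible reason for weighting. All of that stands: no amendment was missed, and weighting is a legitimate choice. It does not rescue SAP 7.12. The protocol names its test, the SAP names another, and the declaration of no deviation is incorrect.

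Three stronger readings are tempting and are not supported.

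- *That the study is underpowered.* The stated figures reproduce. The table shows weighting moving power either way, depending on a noise share that the documents do not give.
- *That the type I error is materially inflated.* The text of Step 4 and the weight formula are blacked out or removed from the public copy. They may already include between-patient variance, an unweighted analysis or the Wilcoxon fallback. Only the 5.0-5.8% range is tied to the documented design, and even that assumes SE-only weights.
- *That the final report will conceal the change.* SAP 7.12 itself repeats the duty to describe and justify changes of method in the study report. The false declaration makes an omission easier but does not remove the duty.

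**Conclusion.** The point holds as a mismatch between Protocol H.1.1, SAP 7.9.1.3 and SAP 7.12. It affects both primary objectives and the non-inferiority decision, and it can be read directly from visible text; high confidence applies to that part only. The section 6 power is correct for the unweighted test and was not derived for the weighted one.

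Any effect on error is conditional. It needs weights from within-patient SE alone, the usual weighted variance with n - 1 df, SEs that differ between patients, and true differences that vary between patients. Error is then about 5.0-5.8% from the AV-delay design alone, and about 7.5-9% at an assumed SE CV of 30% when half or more of the variance is between patients. It stays near 5% if the weights include between-patient variance or if all spread is noise. Severity is minor to should-fix.

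**What to change.** 1. Correct SAP 7.12 to list the weighted t-test as a change from Protocol H.1.1, with its reason.
2. Name one test as primary for both primary objectives and for the non-inferiority interval, and report the other as a sensitivity analysis. The unweighted paired t-test, with its Wilcoxon fallback, is the natural primary: the power was computed for it, and it holds its error rate without depending on the spread of SEs.
3. If the weighted test stays primary, its weights should include between-patient variance, unless the unseen text already provides for this. The SAP should then say that the section 6 power refers to the unweighted test.

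This costs SAP wording and a few lines of code; the data are the same. The downside of an unweighted primary is lost efficiency if measurement noise dominates the 7% SD. If all of it were noise, 1/SE² weights would reach 82%, 86% and 92% power for objective 1 at SE CVs of 10%, 20% and 30%, against 81% unweighted. If half were noise, weights that include between-patient variance would reach 81%, 82% and 84%.
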